5.2 Patient Registration and Enrollment

Patients must have signed and dated all applicable consents and authorization forms to be registered in the Clinical Trials Management System (CTMS) system, which is sponsored by The University of Oklahoma Stephenson Cancer Center (OU-SCC).

First, the study site should send the required documentation to [contact] for confirmation of eligibility. A Screening identification (Screening ID) number will be provided by OU-SCC research staff. After all screening procedures and assessments have been completed and eligibility has been established, the subject Study ID number will be generated by OU-SCC. Once the patient has been provided a Study ID number, only the Study ID number should be used.

Patients must not start protocol procedures prior to registration and enrollment. A patient will start protocol procedures only after the pre-treatment evaluation is complete and eligibility criteria have been met.

NOTE: Per the Institutional Review Board (IRB) reporting, a patient is considered accrued once he or she signs a consent form for the study. A patient is considered enrolled once the patient begins treatment.

6.0 Study Outcomes and Study Measures

6.1 Primary Outcome

- 6.1.1 Adverse events as characterized by CTCAE v5.0 in patients that may result from MSOT imaging ($\geq 44^{\circ}\text{C}$)¹³
- 6.1.2 Measurement of skin temperature pre- and post-MSOT imaging (pre- and post-surgery 4 measurements total) with a touch thermometer as part of the safety evaluation of the MSOT device. The thermometer will be placed onto the skin until a temperature appears, about 1 minute, and the temperature will be recorded.

6.2 Secondary Outcomes

- 6.2.1 Tumor positivity as based on standard clinical laboratory techniques and signal detection of oxy- and deoxy-hemoglobin using MSOT localization
- 6.2.2 Tumor volumes as estimated by MSOT and by standard clinical laboratory techniques
- 6.2.3 Identification of tumor and/or lymph nodes based upon either Isosulfan Blue or IC Green dye

7.0 Study Plan

7.1 Study-Related Activities

Study Procedures

- Upon receipt of a signed consent form, the research study team will generate a unique identification number so that subjects are de-identified for analysis of data. *Any standard imaging measurements will be added in [Appendix A and B](#).* This unique identification number will be used on the case report form ([Appendix A and B](#)).
- Patients will go through standard care procedures to prepare for surgery. Medically established diagnostic procedures will be used to detect tumor and lymph node margins.
- To evaluate the safety of MSOT ([Figure 2](#)), the device will be used to obtain images of the tumor or lymph node margins for investigational use only to compare to clinical pathology and patient's medical record.
- As part of the standard of care surgery preparation for cancer resection for all tumor types, patients will be injected with standard doses of Isosulfan Blue/ Indocyanine (IC) Green for either lymph node or tumor identification as part of the standard surgical procedure. The MSOT device will detect the presence of dye at the standard dose of dye used for surgical evaluation of tissue.

Figure 2 The MSOT Acuity

- Images will be obtained pre- and post-surgery (example simulation of operating room shown [Figure 3](#)). All imaging will be done in a closed surgical patient; no imaging will be performed on an open surgical patient. [name] has been trained in the use of the MSOT Acuity by the manufacturer, and she will be the MSOT operator for all MSOT imaging for this study. [name] will train the surgeon and surgical staff in the proper procedure for using the handheld

[figure not shown]
[figure not shown]
[figure not shown]
[figure not shown]
[figure not shown]
Figure 3: Demonstration of MSOT scanning procedure. A. Handheld detector covered with drape; B. surgeon; C. MSOT Acuity; D. trained MSOT operator.

detector and will maintain training records for this purpose. Only [name] and her research staff will perform post-imaging analysis on the de-identified digital images stored on the MSOT Acuity. The pathologist and clinician will perform all clinical evaluations of tumor samples as well as post-imaging assessment of treatment area and report where indicated on the imaging case report form. MSOT imaging will be for research only and no treatment decisions will be based on the MSOT images obtained.

- Logistics: The MSOT device will be used in The University of Oklahoma Health Sciences Center (OUHSC), and will reside in a temperature controlled and locked room.

Table 2 Clinical Protocol for MSOT Imaging

Step	Description
1	Prior to the time of surgery, the MSOT operator will ensure that the MSOT Acuity has been cleaned according to the manufacturer's recommendations found in the Instruction Manual -MSOT Acuity Cleaning & Disinfection.
2	A case report form with a unique identification number will be generated for each study participant (Appendix A).
3	The MSOT operator will maneuver the MSOT Acuity to the operating room and plug unit into proper electrical outlet. The MSOT Acuity will be positioned to allow easy access to the region of interest for imaging. The wheels will be locked into place to prevent acquisition unit from rolling during imaging.

4	The adjustable arm holding the monitor and keyboard will be locked into position for use by the MSOT operator for image acquisition.	
5	The MSOT operator will turn the key on the front panel to switch on the Acuity system, wait until the logon screen appears and log in.	
6	Following the login, ViewMSOT™ automatically starts, initializes the hardware and opens the Select patient dialog.	
7	The MSOT operator will create a new patient record using the unique identification number as the Patient ID.	
8	The MSOT operator will Click on the Examination tab in the task bar to open the Examination screen.	
9	The Select preset* window will open, and the MSOT operator will choose the Hb, HbO _{melanin} application to access the Examination screen. Check box when complete on Imaging Case Report form. *NOTE: Wavelengths and power settings are factory preset and cannot be changed manually by the user.	
10	The system performs an automatic system self-test each time the Examination screen is accessed for the first time after the system was switched on.	
11	The transducer must remain in the magnetic probe holder fixed to the acquisition unit until the system self-test has been completed. If the ultrasound probe is not in the probe holder, the MSOT operator will make sure that it is placed there.	
12	The staff will don safety goggles. The MSOT operator can control laser activation and deactivation via touch screen or keyboard in combination with the connected foot pedal.	

13	The MSOT operator will hold the foot pedal until the self-test routine is finished. If the self-test is interrupted by releasing the foot pedal before the system self-test has been finalized, the test routine will need to be performed again.
14	
A blue indicator in the signaling device on top of the system and in the front panel shows that the laser is ready for emission.
 
15	
The MSOT operator will record the self-test completion on the case report form and note the Start scan time.
 
NOTE: THE FOOT PEDAL WILL BE RELEASED ONCE SELF-TEST ROUTINE IS COMPLETE.

16	The MSOT operator will tell the surgical team when the self-test routine has been successfully completed.
17	
The MSOT operator will remove the probe from the magnetic holder to disinfect it using a germicidal disposable wipe (Sani-Cloth AF3, PDI, Orangeburg, NY), ensuring that the entire surface of the probe is moistened with the disinfectant.
 
18	
The MSOT operator will remove a second wipe from the package and repeat the disinfection process, ensuring that the entire surface of the probe is moistened with the disinfectant and allowed to dwell for at least 3 minutes.
 
NOTE: MSOT Operator will note dwell time on Imaging Case Report Form (Appendix A).

19	After the 3-minute exposure time of the disinfectant, the MSOT operator will dry the probe surface with a commercially available, single-use, lint-free, low-germ towel.
20	A member of the surgical team will cover the handheld probe with a single-use ultrasonic probe drape (US.10.150.080, SonoGuard, Promecon GmbH, Hamburg, Germany), which will be the only part of the Acuity device to make contact with the patient, see (Figure 3).
21	Once time-out procedures have been completed, the surgical team will prepare the patient/region of interest on the skin for the initial MSOT scanning.
22	The skin surface will be cleaned following standard procedures. The skin will be dry without any alcohol pooling per manufacturer instructions, then ultrasound gel (#03-034, Aquasonic clear ultrasound gel, Parker Laboratories, Inc., Fairfield, NJ) will be applied to the area to be scanned.
23	The surgeon will place the imaging probe on the prepped skin area to be imaged BEFORE the laser is activated to avoid excess laser radiation.
24	Once the surgeon has the probe in place, the MSOT operator will press the foot pedal to activate the laser radiation for imaging. The MSOT operator will communicate with the surgeon as an image is acquired and coordinate the timing of the laser activation for additional scans. Release of the foot pedal will immediately shut down the laser system and stop the imaging procedure.
25	
The MSOT operator will record Scan comments on the screen to be saved for each image acquired in the image sequence.
 
NOTE: Total number of images acquired in the image sequence will be recorded on the Imaging Case Report Form (Appendix A).

26	
A yellow indicator in the signaling device on top of the system and in the front panel shows that laser light is emitted through the aperture of the handheld probe. Keep the aperture of the probe on the region of interest or towards the floor. NEVER direct the aperture of the probe towards eyes while this indicator is on. Once the foot pedal is released laser emission is stopped and the laser emission indicator will turn off.
	
27	The patient will undergo surgery for resection of the identified volume of tissue according to standard care.	
28	After tumor or lymph node removal and incision has been closed, the area of interest will be reimaged by MSOT to obtain post-surgery images in the operating room by repeating steps 16 through 23.	
29	An estimate of the percent amount of tumor remaining will be estimated by algorithms within in the MSOT computer programming for investigational use only.	
30	The resected tumor will be taken to Pathology for volume assessment and pathological identification per medically established diagnostic standard care.	
31	Data from the MSOT imaging is for research purposes only and not for treatment, and digital images will be kept on the MSOT computer, which will be stored in a secured room accessible only to study personnel.	
32	Key parameters will be recorded on (Appendix A and B).	

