Imaging of tumors and cancer-related morphologic changes in tissues by MSOT is facilitated through exogenous contrast agents, including clinically approved optical dyes (e.g., isosulfan blue or indocyanine green)⁸, markers targeted to cell surface molecules, for example, EGFR¹¹, the tumor microenvironment (e.g., pH)⁹, and endogenous absorbers (i.e., oxyhemoglobin)^{2,10}. Use of MSOT in multiple tissue types and at varying depths, i.e., at least 5 cm^{3,8}, can provide functional real-time three-dimensional (3D) information at high spatial resolution *in vivo*¹. This ability will have a significant impact on clinical care in systemic diseases, including cancer involving multiple organs. The ability of MSOT to identify tumors indicates great potential for clinical applicability for solid tumors, such as melanoma, head and neck, breast, pancreatic, prostate, colon, and potentially, liver cancer.

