- ix. Patients with Stage IV pancreatic cancer, Stage IV HNSCC are not surgical candidates and therefore excluded from this study

5. Analysis Populations

- **Safety population:** All subjects who received MSOT readings will be included in the overall safety analysis, with toxicities graded according to NCI CTCAE v5.0. This is primarily a safety analysis study.

6. Summary of Study Population

a. Patient Disposition

- i. Descriptive statistics on the demographics and presenting features will be calculated. Proportions will be calculated for categorical variables and medians with the minimum and maximum will be calculated for continuous variables.

7. Safety Analyses

a. Adverse Events

- i. The severity of the AE will be graded by the Investigator using the NCI CTCAE, version 5.0.
- ii. The adverse events will be estimated by grade, type and relatedness. The first analysis will pool all grade 3 unexpected events that are possibly, probably or

definitely related to MSOT together and then construct a 95% exact Clopper-Pearson binomial confidence interval for this estimate.

b. Temperature Analysis

- i. Measurement of skin temperature will be evaluated where skin temperature greater than 44°C will be recorded and a 95% exact Clopper-Pearson binomial confidence interval constructed.

c. Secondary Analysis

- i. Tumor positivity from pathology reports and MSOT readings will be compared and Pearson correlation coefficient created.
- ii. Deoxy- and oxy-genation levels will be compared to non-tumor values from the same patient. Paired t-tests will be used to compare the values and a Wilcoxon Signed Rank test performed. Median and interquartile range will be reported.

8. Handling of Missing Data

Every effort will be made to collect information at all defined visits including at early withdrawal or dropout. Reasons for missing data will be summarized. However, there will be no imputation of missing data.

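### Protocol Table 2 and Appendix A name different imaging presets, and neither document says how injected dye is kept out of the hemoglobin results

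*Protocol*

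**What the plan says.** **Dye.** Protocol 7.1 says, for all tumor types, that "patients will be injected with standard doses of Isosulfan Blue/ Indocyanine (IC) Green for either lymph node or tumor identification", and that the device is expected to see it: "The MSOT device will detect the presence of dye at the standard dose of dye used for surgical evaluation of tissue". Protocol 2.1 lists "clinically approved optical dyes (e.g., isosulfan blue or indocyanine green") among the contrast agents for MSOT, and says the method tells absorbers apart by the shape of their spectra.

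**Preset.** In Table 2 step 9, "the MSOT operator will choose the Hb, HbO _{melanin} application" (that is, Hb, HbO and melanin), with the note that "Wavelengths and power settings are factory preset and cannot be changed manually by the user". Step 9 also has the operator tick a box on the imaging case report form, which is Appendix A. The box in Appendix A section 7 names a preset with Hb, HbO, Isosulfan Blue and/or ICG, and no melanin. Step 28 has the post-surgery scan repeat steps 16 to 23 only.

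**Endpoint and analysis.** Outcome 6.2.1 sets pathology against "signal detection of oxy- and deoxy-hemoglobin using MSOT localization"; dye identification is a separate outcome (6.2.3). Protocol 10.2 treats tumor positivity and dye positivity as separate yes/no measures. SAP 7.c.i correlates MSOT positivity with pathology. SAP 7.c.ii says: "Deoxy- and oxy-genation levels will be compared to non-tumor values from the same patient", using paired t-tests and a signed rank test. None of these analyses mentions dye status, dye type or the components of the spectral separation.

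**Forms.** Appendix A items 1e and 1f record whether a dye was used during surgery and which one, but not when. Appendix B gives Hb, total Hb and HbO separate pre- and post-surgery entries, and gives each dye one row that is not split by scan.

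**The concern.** By the protocol's own account the dye is an MSOT absorber, and it is given to mark the tissue being imaged. If a separation has no component for an absorber that is present, part of that absorber's signal will usually be credited to components that are in the model. Here those would be oxy- and deoxy-hemoglobin.

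At stake is secondary objective 3.2.2. A tumor versus non-tumor difference in SAP 7.c.ii, or an MSOT-positive call under 6.2.1, could reflect dye uptake and be reported as endogenous hemoglobin contrast. The forms would not allow this to be untangled afterwards. A ticked box does not show which of the two presets was used, one box covers both scans, and dye status at each scan is not recorded.

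**Working it through.** **1. The two preset instructions**

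| Source | Components named | Dye component? |
|---|---|---|
| Table 2 step 9 | Hb, HbO, melanin | No |
| Appendix A section 7 | Hb, HbO, Isosulfan Blue and/or ICG | Yes, but which one is left open |
| Step 28 (post-surgery) | Repeats steps 16–23; step 9 not revisited | As set for the first scan |

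The first two rows cannot both describe the same selection.

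**2. What leaving dye out does to a fit**

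Write the measured spectrum as *y = Xb + d·c*. Here *X* holds the spectra in the model, *b* the true Hb, HbO and other amounts, *d* the dye spectrum and *c* the dye amount. An unconstrained least-squares fit without *d* has expectation *b + (X′X)⁻¹X′d·c*. The error is proportional to *c*, and its sign depends on the shape of *d* relative to *X*. The documents give no spectra, wavelengths or fitting method, so neither sign nor size can be derived.

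Trial fits with assumed spectra make the same point. With a true saturation of 60% and an omitted dye adding 10% to the blood signal, a dye band peaking at 640 nm gave an apparent saturation of 41% under one set of assumed spectra and 100% under others. With dye in the model and no noise, the fit returned 60%.

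**3. Why pairing does not remove it**

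Let *a* be the error per unit of dye, with *c_T* and *c_N* the dye in tumor and non-tumor tissue. The paired difference is

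(H_T + a·c_T) − (H_N + a·c_N) = (H_T − H_N) + a·(c_T − c_N).

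The last term vanishes only if *a* = 0 or dye is equal in both tissues. A dye meant to identify the target is not expected to be equal in both.

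**4. What an offset would do to the SAP 7.c.ii t-test (illustration)**

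The documents state no figure for this test. Protocol 10.2 gives 80% power for a paired t-test on tumor volume, so the formula was checked there first. Power is the two-sided 5% rejection probability of a noncentral t with n − 1 df and noncentrality δ√n.

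- n = 50, δ = 0.4: noncentrality 0.4 × 7.07 = 2.83, power 79.2%.
- n = 45, δ = 0.43: power 80.5%.

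Both agree with the plan's 80%. Now let the true Hb/HbO difference be zero and δ be a constant dye offset in SDs of the paired difference. This assumes every patient contributes a pair and is equally affected.

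| Offset (SD) | Rejects, n = 50 | Rejects, n = 45 |
|---|---|---|
| 0 | 5.0% | 5.0% |
| 0.1 | 10.7% | 10.1% |
| 0.2 | 28.4% | 25.9% |
| 0.3 | 54.8% | 50.3% |
| 0.4 | 79.2% | 74.7% |
| 0.5 | 93.4% | 90.7% |

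If only half the patients had dye in the target, an individual offset of 0.4 SD would average 0.5 × 0.4 = 0.2 SD, near the 0.2 row. The true offset could be zero.

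**5. Is dye present at the scan?**

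Protocol 7.1 places injection in surgery preparation. Table 2 has no injection step. Appendix A asks about dye during surgery, and its yes/no form allows for patients without dye. Dye at the pre-surgery scan is therefore possible but not stated.

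**The case against.** The strongest reply is that the protocol does provide for dye. The box that step 9 tells the operator to tick names a preset with dye components, and Appendix B lists each dye as an MSOT parameter apart from Hb, total Hb and HbO. If the Appendix A preset is what is used, the route to error is much weaker. That stands, and it is why the point is conditional. It does not settle the matter, because the operating instruction says something else and neither analysis section says which applies.

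Second, a preset need not be the separation model. The step 9 note speaks of wavelengths and power, and research staff analyse stored images later. This also stands. A dye component might be added afterwards, but no text says so, and the acquired wavelengths that would have to support it are not listed.

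Third, exposure is uncertain. Injection time is not recorded, and 7.1 allows dye for lymph nodes alone, so dye in the tumor cannot be assumed. This stands and limits what can be claimed.

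Fourth, this is a secondary outcome in a study the SAP describes as primarily about safety, and no treatment decision rests on the images. This limits the weight of the point but does not remove it.

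**Conclusion.** The point holds in conditional form. The preset instructions conflict, and no analysis text says how dye is separated from hemoglobin. Following step 9 and SAP 7.c.ii as written could report dye in the target as a hemoglobin difference. This should be corrected for 6.2.1 and SAP 7.c.ii. It does not touch the primary safety outcomes.

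The conclusion rests on two assumptions: that dye is in the imaged target at the scan, unequally with comparison tissue, and that it has no component in the separation. The rejection rates above show sensitivity to an assumed offset and do not estimate one.

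A reader might infer more, but the documents do not support these stronger readings:

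- **That the study's preset excludes dye, so the results are contaminated.** Appendix A and Appendix B point the other way.
- **That the error falls mainly on the pre-surgery image.** Injection time relative to that scan is not given.
- **That a pre- versus post-surgery hemoglobin test is biased.** Neither Protocol 10.2 nor SAP 7.c specifies such a test.
- **That a given share of patients would be misclassified, or that the two dyes bias in opposite directions.** There are no spectra, and no signal cutoff for a positive call, from which to work this out.

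**What to change.** 1. Reconcile Table 2 step 9 with the Appendix A check box so that both name the same preset, and state in step 28 which preset applies to the post-surgery scan.
2. State in Protocol 10.2 and SAP 7.c that Hb and HbO from any scan with dye present are computed with the injected dye as a separate spectral component.
3. Add to Appendix B, for each of the two scans, whether dye had already been given and which one. Use and type are already on Appendix A (1e, 1f); status at the scan is what is new.
4. Report the 6.2.1 and SAP 7.c.ii results by dye status at the scan (none, Isosulfan Blue, IC Green) as a sensitivity analysis where group sizes allow. If nearly all patients receive dye, the no-dye group may be empty, and item 2 must carry the correction.

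The cost is wording in both documents, one added form entry per scan, and possibly re-processing stored images, provided the acquired wavelengths can resolve the dye. Estimates become slightly noisier with one more component, and groups within at most 50 patients will be small. No change to dye dose or timing is proposed.

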8.4 Unanticipated Adverse Device Effects Reporting Requirements

Unanticipated Adverse Device Effect (UADE) means any serious adverse effect on health or safety or any life-threatening problem or death caused by, or associated with, a device, if that effect, problem, or death was not previously identified in nature, severity, or degree of incidence in the investigational plan or application (including a supplementary plan or application), or any other unanticipated serious problem associated with a device that relates to the rights, safety, or welfare of subjects.

A medical review shall immediately occur with all reported Unanticipated Adverse Device Effects (UADE). The UADE shall be assessed for an unreasonable risks' determination. If an unreasonable risk has been determined, then the trial or the parts that cause the risk shall be stopped between 5-15 working days after making the determination.

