10.0 Statistical Considerations

10.1 Analysis of Primary Objective

10.1.1 The primary objectives are to estimate the rate of adverse events and measure the skin temperature change following MSOT imaging both pre- and post-surgery. The adverse events will be estimated by grade, type and relatedness. The first analysis will pool all grade 3 unexpected events that are possibly, probably or definitely related to MSOT together and then construct a 95% exact Clopper-Pearson binomial confidence interval for this estimate. Additionally, measurement of skin temperature will be evaluated where skin temperature greater than 44°C will be recorded¹³. A 95% exact Clopper-Pearson binomial confidence interval for the evaluation of skin temperature will be conducted

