Appendix A – Imaging and Tissue Data Collection Form

Study Number: OU-SCC-MSOT PID: 0 1 - _____

Investigator: [name] Surgery Date: ____/____/____

1) Tumor or Lymph Node Assessments:

a) Target tissue

Tumor

Lymph Node

b) Standard of care method of imaging

MRI _____ tumor amount

PET _____ tumor amount

CT _____ tumor amount

Other: _____ tumor amount

c) Did patient receive neoadjuvant therapy?

Yes

No

d) MSOT Image acquired?

Yes

No

e) Was an indicator dye used during surgery?

Yes

[figure not shown]
No

f) If an indicator dye used during surgery, please indicate which dye.

Isosulfan Blue IC Green

2) Location of Imaging

a) Please circle the location of the imaging (below) and provide further description as necessary

[https://anatomyclass123.com /](https://anatomyclass123.com/)

b) Erythema post-MSOT Imaging (RTOG)

i. Time after imaging: (hr: min) _____

ii. Grade (RTOG)

- 0 No erythema present
- 1 Follicular, faint or dull erythema, epilation, dry desquamation, decreased sweating
- 2 Tender or bright erythema, patchy moist desquamation, moderate edema
- 3 Confluent, moist desquamations other than skin folds, pitting, edema
- 4 Ulceration, hemorrhage, necrosis

3) Clinical Pathology Assessment

a) Date or diagnosis (month / year):

b) Positive tumor tissue:

Yes No
 c) For Pancreatic melanoma breast HNSCC ovarian (check one) indicate stage at diagnosis (**TNM classification**):

Tx T0 Tis T1 T2 T3 T4
 Nx N0 N1 N2 N3
 Mx M0 M1

d) Tumor subtype (if applicable) _____

4) Skin temperatures

Pre-Surgery MSOT imaging			
Pre-imaging Skin Temperature (°C)		Time	
Post-imaging Skin Temperature (°C)		Time	

Post-Surgery MSOT imaging			
Pre-imaging Skin Temperature (°C)		Time	
Post-imaging Skin Temperature (°C)		Time	

5) Patient Monitoring (*)please note that patients must be monitored daily for adverse events until discharge). Please answer yes or no if Erythema at grade III or higher or change in skin pigmentation occurs.**

Yes No

_____ Post surgery	_____ 8 day
_____ 1 day	_____ 9 day
_____ 2 day	_____ 10 day
_____ 3 day	_____ 11 day
_____ 4 day	_____ 12 day
_____ 5 day	_____ 13 day
_____ 6 day	_____ 14 day
_____ 7 day	_____ 15 day

Discharge date: _____

6) Adverse event. Please answer yes or no if Erythema at grade III or higher or change in skin pigmentation occurs.

Yes No

If yes, please fill out details below:

_____ Erythema _____ Time _____ Date

_____ Changes in skin pigmentation _____ Date

7) MSOT Scan Times:

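### The post-surgery MSOT scan does not depend on how the patient responded to the first scan, although skin temperature after that scan is measured

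*Protocol*

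**What the plan says.** Protocol 7.1, Table 2, step 28 governs the second scan. Once the tissue is removed and the incision closed, "the area of interest will be reimaged by MSOT to obtain post-surgery images in the operating room by repeating steps 16 through 23".

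Information on the patient's response to the first scan is partly collected:

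- Protocol 6.1.2 lists as a primary outcome "Measurement of skin temperature pre- and post-MSOT imaging (pre- and post-surgery 4 measurements total"). Appendix A item 4 has a separate, timed field for the reading after the pre-surgery scan.
- Protocol 7.1 has the pathologist and clinician carry out "post-imaging assessment of treatment area and report where indicated on the imaging case report form".
- Appendix A item 2b, "Erythema post-MSOT Imaging (RTOG"), asks for one grade and one time after imaging, and does not say which scan it refers to. Item 6 reads "6) Adverse event. Please answer yes or no if Erythema at grade III or higher or change in skin pigmentation occurs", again without naming the scan. The daily checklist in item 5 begins after surgery.

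The use made of the temperature is in Protocol 10.1.1: it is evaluated "where skin temperature greater than 44°C will be recorded", with a 95% Clopper-Pearson interval. SAP 7.b says the same.

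On the purpose of the scans, Protocol 7.1 states that "MSOT imaging will be for research only and no treatment decisions will be based on the MSOT images obtained".

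**The concern.** Safety is the primary objective, and 44°C is the plan's own thermal threshold. Yet a patient who reaches it after the first scan is, on the text, scanned again over the same area a few steps later. The same holds for a severe skin reaction. The second exposure guides no treatment, so withholding it costs the patient no clinical benefit.

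The reading needed for the decision already exists when the decision falls due. What is missing is the link between the two. For skin findings the gap is slightly wider, because a single unlabelled erythema entry does not guarantee a separate record of the skin between the scans.

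**Working it through.** **1. Does any repeated step look at the patient's response?** Steps 16 to 23 cover notice that the self-test passed (16), probe disinfection and drying (17–19), the drape (20), time-out and preparation (21), skin cleaning and gel (22), and probe placement before the laser is activated (23). None checks temperature or skin. Table 2 contains no temperature step at all.

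**2. What is known before the second scan?** Three of the four temperatures: before scan 1, after scan 1, and before scan 2. No rule uses any of them.

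**3. Does another section supply the rule?**

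- 4.2.8 (increased risk) is an exclusion criterion applied at entry.
- 7.3 allows withdrawal on request, or removal for progression that rules out surgery, and recognises no other reason.
- 8.4 says "A medical review shall immediately occur with all reported Unanticipated Adverse Device Effects", but this concerns serious effects, and its stopping rule applies to the trial or parts of it, 5–15 working days after a determination.
- 8.6 makes post-imaging effects beyond the normal reportable adverse events, in the investigator's opinion. It does not govern the next scan.
- The DSMC's authority (9.0), the 10-patient review (10.3) and the grade V halt (10.3.2) act on the study.
- The SAP adds nothing on this.

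**4. How often would a rule apply?** The documents give no base rate for 44°C, so that frequency is unknown. For grade III–IV events, 10.3.2 cites none in over 600 patients. With x = 0, the exact two-sided 95% upper limit is 1 − 0.025^(1/n).

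- Check against the plan (10.3.1): n = 50 gives 1 − 0.025^(1/50) = 7.11%, matching its 7.1%.
- n = 600 (taking the stated figure as a floor): 1 − 0.025^(1/600) = 0.61%. In 50 patients that is 50 × 0.0061 = 0.31.

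This 0.31 is a ceiling for all grade III–IV events, whenever they appear. Reactions visible before the second scan would be fewer.

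**5. What would a rule cost the analysis?** Suppose one of 50 patients is withheld for temperature and there are no other events. For x > 0 the upper limit is the 0.975 quantile of Beta(x + 1, n − x).

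- Per-patient temperature rate over either scan: this patient is already an event, so the result is 1/50 with or without the second scan (upper limit 10.65%).
- Post-surgery-only rate: 0/49 gives 7.25%, against 7.11% for 0/50, or 1/50 (10.65%) if the withheld scan counts as an event. Neither 10.1.1 nor SAP 7.b calls for this rate.
- With two withheld, the post-surgery rate runs from 0/48 (7.40%) to 2/50 (13.71%).
- Adverse event rate: the patient stays in the denominator with one exposure, so the 50 patients contribute 99 scan sessions instead of 100.

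**6. Is the threshold itself stated consistently?** 6.1.1 and SAP 2.a use ≥44°C; 10.1.1 and SAP 7.b use greater than 44°C. A reading of exactly 44.0°C falls on different sides. The first line of step 5 holds for such a reading only if ≥44°C is used throughout.

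**The case against.** The strongest reply is that the second scan is already surrounded by safeguards. The repeated steps include confirmation of the self-test and placing the probe before activation so as to limit laser exposure. Power is factory preset (step 9), and releasing the foot pedal stops emission (step 24). Protocol 6.1.1 attaches ≥44°C to adverse events, 8.0 has every adverse event assessed, and 8.6 relies on medical judgement. The surgeon holds the probe and can decline a research scan. Only mild, reversible skin effects are expected.

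Most of this stands, and it limits the point. A reader might infer that the second scan has no safety condition of any kind, or that clinicians are obliged to scan an injured patient. The documents support neither: device checks are repeated and judgement is available. What they lack is a condition based on the patient's response, and a criterion to guide that judgement.

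A reader might also infer from the 16–23 range that the laser is never activated after surgery, since activation is step 24. Re-imaging plainly implies activation, so this is a cross-reference slip. It matters only because the image count and eye-safety instruction (steps 25–26) also fall outside the range.

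Two objections concern the remedy. Edema and hemorrhage appear in the RTOG grade descriptions and can follow from surgery itself, so a skin trigger assessed after closure would cancel scans for the wrong reason. It must be assessed before incision and attributed to MSOT. And withholding removes second exposures from the patients who heated most, so the adverse event rate no longer describes two scans in everyone. Both are accepted and shape the fix.

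**Conclusion.** The point holds as a modest participant-safety gap. The plan measures a relevant response to the first scan, names a threshold for it, and then orders the second scan without reference to either.

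For an affected patient, a rule would reduce MSOT sessions from two to one. The number affected is expected to be close to zero. The ceiling of about 0.3 in 50 applies to grade III–IV events and assumes the cited experience carries over to this device use. It says nothing about 44°C readings, whose frequency is unknown.

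It would be wrong to infer that the missing rule biases the planned per-patient adverse event rate, or that harm is likely. Every scanned patient stays in the SAP section 5 safety population, and the documents give no evidence of frequent heating. The case for change rests on low cost and on a research-only exposure that the patient does not need.

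**What to change.** 1. **Step 28.** Withhold the post-surgery scan if the temperature after the pre-surgery scan is ≥44°C. Also withhold it for a skin reaction of RTOG grade 3 or higher, assessed after the first scan and before incision and judged at least possibly related to MSOT. Adverse events remain graded by CTCAE v5.0.
2. **Recording.** Record temperature and erythema after each scan, label the erythema field in Appendix A by scan, and add a field for post-surgery scan withheld, with reason. Extend the step 28 range to include steps 24–26 and the new recording step.
3. **Follow-up.** State that withholding a scan is not removal from the study. The patient stays in follow-up and in the safety population.
4. **Threshold and reporting.** Use ≥44°C in 6.1.1, 10.1.1, SAP 2.a and SAP 7.b. State in the report how many patients had one scan and how many had two.

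The cost is a few clauses in Table 2, a label and a field on the form, one sentence on follow-up and a short SAP edit. The sample size does not change, and temperature is already collected for each scan. The drawback is that a few post-surgery images and temperatures may be lost, with no imputation under SAP section 8. Withheld patients would also contribute a single exposure to both the temperature and the adverse event rates.
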